### **Study Day**

**Study Day 1** is defined as the first IMP dose date. For patients who are randomized but not dosed after randomization, Study Day 1 is defined as the date of randomization.

**Study Day** is defined as the number of days from Study Day 1.

*Before Study Day 1:*

$$\text{Study Day} = (\text{Date of Interest} - \text{Date of Study Day 1})$$

*On or after Study Day 1:*

$$\text{Study Day} = (\text{Date of Interest} - \text{Date of Study Day 1}) + 1$$

Therefore the day prior to Study Day 1 is -1.

### **Baseline**

The baseline period for efficacy endpoints collected by the eDiary (e.g. monthly migraine days) is defined as the period between the eDiary device assignment date and the day prior to study day 1 (study day one is not included).

A baseline for PROs (for SF-36v2, HIT-6, BDI-II) and safety endpoints (including C-SSRS) refers to the last evaluable measurement prior to or on the study day 1.

Note: Assessments on the day of randomization are assumed to have been taken as per protocol, i.e. if the assessment should be performed before dosing, the assessment will be treated as pre-dose as per protocol. Practically, i.e. that the time part of the date/time entry will be ignored.

Exception: In case there is a protocol deviation or a comment that specifically indicates that the assessment has been taken post-dose, the assessment will not be treated as pre-dose.

**Patient-level End of Study (EoS) Date**

The end of study (EoS) date for each subject is defined as the last date on which the subject participated in the study. The date will be recorded on the Study Completion eCRF page.

**2.1.1.2 Visit and analysis window**

Since the actual visit for a subject may not exactly coincide with their targeted visit date, the actual visit date is mapped to a study visit.

The nearest study day window will be utilized to define study visit for lab, vital signs, ECG, C-SSRS and some PROs collected during office visits (HIT-6, SF-36v2, ██████████) before dose is administered.

**Table 2.1.1.2-1. Study Visit Windows in the DBTE**

Study visit	Target day	Study Day
Week 0	1	1
Week 1	8	2 - 11
Week 2	15	12 - 18
Week 3	22	19 - 25
Week 4	29	26 - 32
Week 5	36	33 - 39
Week 6	43	40 - 49
Week 8	57	50 - 70
Week 12	85	71 - 98
Week 16	113	99 - 126
Week 20	141	127 - 154
Week 24	169	155 - 182

**2.1.1.3 Demographics and other baseline characteristics**

**Beck Depression Inventory II (BDI-II)**

The BDI-II is a 21-item questionnaire that assesses severity of depression with the recall period of two weeks, including the day of completion. Each item is scored from 0 to 3. The total score varies between 0 and 63 and can be categorized into 4 severity grades:

- minimal depression (0-13)
- mild depression (14-19)

- moderate depression (20-28)
- severe depression (29-63)

The BDI-II is completed once during the study at screening visit via eDiary. Moderate and severe depression belong to the study exclusion criteria.

Please refer to [BDI-II scoring](#) for scoring details.

#### 2.1.1.4 Efficacy endpoints

##### eDiary

Patients record the efficacy information using the provided eDiary platform. If a patient did not make a contribution to the eDiary at a particular day, it is possible to provide information retrospectively (**retro diary**). In this case, by the next eDiary usage a patient will be first asked to provide information on up to 48 hours prior to the time of completion of this diary and then about the actual state.

##### eDiary Day

A calendar day to which the information from the eDiary refers. Please refer to [Appendix A: Calculation rules](#) for calculation details.

##### Headache Day

A headache day is any calendar day on which the subject experiences a qualified migraine or non-migraine headache (initial onset, continuation or recurrence of the headache). Please see exceptions in [Appendix B: MMD derivation, exceptions](#). A qualified headache is defined as:

- a qualified migraine headache or
- a qualified non-migraine headache, which is a headache that lasts  $\geq 30$  minutes and is not a qualified migraine headache, or
- a headache of any duration for which acute headache treatment is administered. Unknown medications (with no available information on the type of treatment) will not be counted as acute headache treatment.

##### Information Day

A day which is either a headache day or an eDiary day.

##### Migraine day

A migraine day is defined as any calendar day in which the patient experiences a qualified migraine headache (onset, continuation, or recurrence of the migraine headache). Please see exceptions in [Appendix B: MMD derivation, exceptions](#). A qualified migraine headache is defined as a migraine with or without aura, **lasting for  $\geq 30$  minutes**, and meeting **at least one** of the following criteria:

- $\geq 2$  of the following pain features:
  - Unilateral
  - Throbbing
  - Moderate to severe

- Exacerbated with exercise/physical activity
- $\geq 1$  of the following associated symptoms:
  - Nausea and/or vomiting
  - Photophobia and phonophobia

If the patient took a migraine-specific medication (i.e., triptane or ergotamine) during aura, or to treat a headache on a calendar day, then it will be counted as a migraine day regardless of the duration and pain features/associated symptoms. In case of a retro diary spanning the last two days, documentation regarding aura will be considered to apply for both days.

**Monthly Migraine Days (MMD)**

Monthly migraine days at baseline are the number of migraine days in the baseline period that are normalized in a 28-day interval. Monthly migraine days after baseline are the number of migraine days between each monthly IMP dose that are normalized in a 28-day interval. Days without eDiary data in each normalized monthly interval will be prorated. Calculation details are described in [eDiary data](#).

**Monthly Intervals for Monthly Migraine Days**

Monthly migraine days will be calculated based on the patient’s IMP dosing schedule defined below using eDiary data collected from beginning of the baseline epoch up to the end of the DBTE.

**Table 2.1.1.4-1. Monthly Intervals for MMD**

Study Epoch	Assessment Time point	Interval Based on Syringe Dose Dates	
		Start date	End date
Baseline Epoch	Baseline	From eDiary device assignment date (i.e. baseline visit)	Day prior to study day 1
Double-Blind Treatment Epoch	Week 4 (Month 1)	
 
• Study Day 1
 
	
 
• Week 4 syringe dose date -1
 
• Study day 28 if Week 4 syringe dose is not received (either missed or IMP discontinued prior to Week 4)
 

	Week 8 (Month 2)	
 
• Week 4 syringe dose date
 
• Study day 29 if Week 4 syringe dose is not received or IMP
 
	
 
• Week 8 syringe dose date -1
 
• Study day 56 if Week 8 syringe dose is not received (either missed or
 

		discontinued prior to Week 4	IMP discontinued prior to Week 8)
	Week 12 (Month 3)	
 
Week 8 syringe dose date
 
Study day 57 if Week 8 syringe dose is not received or IMP discontinued prior to Week 8
 
	
 
Week 12 syringe dose date -1
 
Study day 84 if Week 4 syringe dose is not received (either missed or IMP discontinued prior to Week 12)
 

	Week 16 (Month 4)	
 
Week 12 syringe dose date
 
Study day 85 if Week 12 syringe dose is not received (either missed or IMP discontinued prior to Week 12)
 
	
 
Week 16 syringe dose date -1
 
Study day 112 if Week 16 syringe dose is not received (either missed or IMP discontinued prior to Week 16)
 

	Week 20 (Month 5)	
 
Week 16 syringe dose date
 
Study day 113 if Week 16 syringe dose is not received (either missed or IMP discontinued prior to Week 16)
 
	
 
Week 20 syringe dose date -1
 
Study day 140 if Week 20 syringe dose is not received (either missed or IMP discontinued prior to Week 20)
 

	Week 24 (Month 6)	
 
Week 20 syringe dose date
 
Study day 141 if Week 20 syringe dose is not received (either missed or IMP discontinued prior to Week 20)
 
	
 
Week 20 syringe dose date + 27 if Week 20 syringe dose is received
 
Study day 168 if Week 20 syringe dose is not received (either missed or IMP discontinued prior to Week 20)
 

**Monthly migraine days over the last three months (months 4, 5, and 6) of the double-blind epoch**

Monthly migraine days over the last three months are calculated as the mean MMD over months 4, 5, and 6. In case of missing data at some time point, mean value will be calculated based on available data.

**Achievement of at least a 50% reduction from baseline in monthly migraine days over the last three months (months 4, 5, and 6) of the double-blind epoch**

A patient achieves at least 50% reduction from baseline over the last three months, if

$$\frac{(\text{Baseline MMD} - \text{average MMD over the last three month of DBTE}) * 100}{\text{Baseline MMD}} \geq 50$$

**Achievement of at least a 50% reduction from baseline in monthly migraine days during the first month of the double-blind epoch**

A patient achieves at least 50% reduction from baseline in the first month of DBTE, if

$$\frac{(\text{Baseline MMD} - \text{MMD in the first month of DBTE}) * 100}{\text{Baseline MMD}} \geq 50$$

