5.5.4 Instructions for prescribing and taking study treatment

The investigational product dose is either 70 mg or 140 mg depending on the investigators decision, which has to be made for each patient individually and in accordance with the product information: the recommended dose is 70 mg, some patients may benefit from 140 mg (see Section 5.1 of AIMOVIG® SmpC).

In case of insufficient response, the dose may be escalated from 70 mg to 140 mg. Possible reasons for up titration could be, but are not limited to:

- insufficient response as deemed by physician and/or patient
- reduction of acute medication use not satisfactory
- insufficient improvement in life quality

An adjustment of the 70 mg dose to 140 mg can be performed at any time during the DBTE. The investigational product dose of 140 mg must not be changed once a patient received the dose during DBTE.

Reference treatment doses are determined during the uptitration phase and must aim to reach the recommended daily treatment dose of 100 mg topiramate in accordance to the German SmPC. The reference treatment dose established during the up titration phase must not be changed during the 18-week maintenance phase.

There are no temporal restrictions for the investigational or the reference treatment (e.g., proximity to meals, sleep or activity).

Test-IMP:

70 mg and 140 mg erenumab or respective placebos will be administered by qualified study staff at each dosing visit during the 24 week double-blind treatment epoch (i.e., at Day 1 and Week 4, Week 8, Week 12, Week 16 and Week 20). Subcutaneous (s.c.) injections are to be given for each investigational product administration. For purposes of study treatment dosing, “q.m.” refers to an every 4 weeks injection regimen. The study drug administration date should be in 4 week increments (+/- 4 days) from the first dose of study drug. Any dose administrations that may occur greater than +/- 4 days from the 4 week time point (e.g., patient unavailability) should be discussed with the Sponsor prior to dosing. The anatomical sites for administration of investigational product are the upper arm, upper thigh, or abdomen; the location of the injection site should be documented in the source document. In order to reduce irritation at the injection site, the investigational product should be stored at room temperature for 30 minutes prior to the administration.

Control-IMP:

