9.4 Analysis of secondary variables

The secondary variable is the achievement of at least a 50% reduction from baseline in monthly migraine days (MMD) over the last 3 months (months 4, 5, and 6) of the double-blind treatment period.

The analysis of the primary variable will be based on the following estimand:

- Population – Full Analysis Set (FAS)
- Variable of Interest: number of patients with at least 50% reduction from baseline in monthly migraine days (MMD)
- Intercurrent event: discontinuation of study medication – effect between erenumab versus topiramate assuming to evaluate treatment policy
- Intercurrent event: discontinuation of study or lost to follow up – effect between erenumab versus topiramate assuming no response could be achieved
- Summary measure – odds ratio

All the subjects’ data collected regarding 50% response of MMD will be used in the analysis regardless whether subjects complete the study drug or not. Subjects with missing response information on this endpoint will be imputed as non-response (non-responder imputation). A logistic regression model including treatment group, baseline value, and stratification factor will be used to perform the treatment comparison (erenumab vs. topiramate) at end of the DBTE. Additional to the odds ratio obtained from the logistic regression, estimates for the risk ratio and the risk difference (with corresponding confidence intervals and p-values) will be calculated for the secondary endpoint.

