## **2.3 Patient disposition, demographics and other baseline characteristics**

### **2.3.1 Patient disposition**

Screening and baseline epoch patient disposition will be based on all screened patients data.

A patient disposition summary for the screening and baseline epoch will include number and percentage of patients, concerning

- Screening  
A patient is defined as screened if signed informed consent is available
- Screening failure  
A patient is defined as screening failure if he was screened but not randomized
- Randomization  
Subjects are considered randomized if they have been assigned a randomization number.
- Non-randomization
  - Reason for non-randomization

The total number of patients screened and the number of patients with screening failure will be summarized, including the reason for screening failure.

The reason for non-inclusion into the study will be listed for screened/baseline patients who discontinued from study prior to randomization.

Patient disposition for the DBTE and follow-up epoch will be presented based on the randomized set (RS).

A corresponding summary will include number and percentage of patients (treatment group specific and overall), concerning

- Completion of double-blind treatment  
A patient is defined as completer for the double-blind treatment if double-blind treatment completion status on the eCRF page is ticked as not prematurely discontinued
- Discontinuation of double-blind treatment
  - Reason for discontinuation of double-blind treatment
- Study completion  
A patient is defined as completer for the study if study completion status on the eCRF page is ticked as not prematurely discontinued
- Discontinuation of the study
  - Primary reason for discontinuation of the study

Protocol deviations (PDs) will be summarized separately for PDs not related to COVID-19 and for PDs related to COVID-19. For PDs not related to COVID-19, the number of patients with at least one PD will be presented (based on RS) and the results of the PDs will be grouped using

the broad categories (Inclusion/Exclusion Criteria (Study eligibility), Withdrawal criteria met, but subject not discontinued, Treatment Deviation, Prohibited Concomitant Medication, Other). For PDs related to COVID-19, the number of patients with at least one PD will be presented (based on RS) and the results of the PDs will be grouped by category of COVID-19 PD and type of relationship to COVID-19.

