## 5 Appendix

### 5.1 Imputation rules

No imputation will be done for missing primary and exploratory endpoints. Subjects with missing response information on the secondary endpoint (achievement of at least 50% reduction from baseline in MMD over the last 3 months (month 4, 5, and 6) of the double-blind epoch) will be imputed as non-response.

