**5.1.2.2 Other imputations**

**5.1.2.2.1 eDiary data**

Missing eDiary data in the calculation of monthly measurements about patients' migraine and non-migraine headaches will be handled using the following method:

1. For **monthly intervals with  $\geq 14$  days of eDiary days** (including retrospective eDiary days) in each interval:

Monthly migraine days will be prorated to 28-day equivalents. Prorated result does not need to be rounded.

2. For **monthly intervals with  $< 14$  days of eDiary use** (including retrospective eDiary days), all monthly measurement will be set to missing.

Monthly Endpoint	Condition	Proration Method (does not need to be rounded)
Monthly migraine days	
If eDiary days in entire baseline or interval post baseline <math>\geq 14</math> (including retrospective eDiary days), then do proration;
 
Else monthly measurement is set to missing
 
[eDiary day is a day with all headache related questions completed retrospectively or not]
	
Number of observed migraine days * 28/ Number of information days in interval
 
[information day is an eDiary day or headache day]

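### The readable SAP does not apply the Protocol 9.4 non-response rule to patients who leave the study late, so an exit from about day 98 can still count as a 50% responder

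*SAP*

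**What the plan says.** Protocol 9.4 names two intercurrent events for the secondary endpoint and handles them differently. Stopping study medication follows treatment policy. For leaving the study or being lost to follow-up, the strategy is "effect between erenumab versus topiramate assuming no response could be achieved". No condition is attached about how much diary data exists. The same section then says that all collected response data are used whether or not study drug is completed, and that missing response information is imputed as non-response.

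The SAP derives the endpoint in steps:

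- **Monthly value (5.1.2.2.1).** With at least 14 eDiary days in the interval, "Monthly migraine days will be prorated to 28-day equivalents"; with fewer, the month is missing.
- **Window (Table 2.1.1.4-1).** Month 4 starts at the Week 12 syringe dose. Month 6 ends at "Week 20 syringe dose date + 27 if Week 20 syringe dose is received", or on day 168 if that dose is not given.
- **Average over months 4 to 6 (2.1.1.4).** "In case of missing data at some time point, mean value will be calculated based on available data".
- **Imputation (2.6.3 and 5.1).** Non-response is assigned to "Subjects with missing response information on the secondary endpoint". Study exit is not mentioned as a trigger.

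**The concern.** Under the SAP, one half-observed month is enough to give a response status. A patient with that much data does not have a missing response, so imputation is not triggered, even if the patient left the study soon afterwards. Protocol 9.4 would make the same patient a non-responder.

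This is the only secondary endpoint, and SAP 2.6.2 attaches a superiority claim to it. If the analysis is programmed as the readable SAP stands, late study leavers are classified by a different rule from the one in the estimand. Late exit need not be equally frequent in the two arms.

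**Working it through.** **1. Monthly grid.** Month m runs from day 28(m − 1) + 1 to day 28m. This reproduces the SAP's own default boundaries: month 4 = days 85–112, month 5 = days 113–140, month 6 = days 141–168.

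**2. First exit day that leaves a response status.** With a complete diary, the 14th eDiary day of month 4 is 85 + 13 = day 98. A last diary day of 97 gives 13 days, so month 4 is missing, no month is available and the patient is a non-responder by imputation. A last diary day of 98 gives 14 days and a valid month. Protocol 5.5.4 states "The study drug administration date should be in 4 week increments (+/- 4 days) from the first dose of study drug", so the Week 12 dose falls on days 81–89 and the threshold on days 94–102. At 80% diary compliance (assumption), 14/0.8 = 17.5, so 18 days are needed: 85 + 17 = day 102, or days 98–106 with the window.

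**3. End of the affected period.** Week 20 dose on day 141 (137–145) + 27 = day 168 (164–172). Exits on days 98–167 are affected: 70 of 168 days, or 42% of the epoch.

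**4. Example.** Baseline 10 MMD; 2 migraine days in days 85–98; then study exit. Month 4 = 2 × 28/14 = 4.0 MMD. Months 5 and 6 are missing, so the mean is 4.0. Reduction = (10 − 4)/10 = 60%. The patient is a responder under the SAP and a non-responder under Protocol 9.4.

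**5. Size per patient.** With about 375 per arm (SAP 1.1), one reclassified patient moves that arm's response rate by 1/375 = 0.27 points. With x responders among n, the log odds change by log[(x+1)/(n−x−1)] − log[x/(n−x)]. For response rates of 30% to 60% (assumption), the odds ratio changes by:

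| Response rate in the arm | Change per patient |
|---|---|
| 30% | 1.27% |
| 40% or 60% | 1.12% |
| 50% | 1.07% |

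The standard error of the log odds ratio, √[1/x₁ + 1/(n−x₁) + 1/x₀ + 1/(n−x₀)], is 0.146–0.159 over that range. It takes 12–15 net reclassified patients in one arm (3.2–4.0%) to move the estimate by one standard error.

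**6. How many leavers that implies.** If 30% to 50% of late leavers meet the criterion (assumption), 12/0.5 = 24 to 15/0.3 = 50 net late leavers are needed, or 6–13% of an arm. Taken the other way, if 1% to 10% of an arm leaves late (assumption), the SAP rule raises its response rate by 0.01 × 0.3 = 0.3 to 0.10 × 0.5 = 5.0 points, about 1 to 19 of 375 patients. The documents give no rate of late study exit.

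**7. Why the end-of-study date cannot date the exit.** Under Protocol 5.6.2, leavers return about 8 weeks after the last dose. After an injection on day 113 that is 113 + 56 = day 169; after day 141 it is day 197. Both fall after month 6. Protocol 5.6.4 lets loss to follow-up be declared only once the scheduled end-of-study visit has passed.

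**The case against.** The strongest reply is that the SAP does follow the Protocol. SAP 2.6.3 repeats the missing-response sentence of Protocol 9.4 almost word for word, and the Protocol summary gives only that rule. On this view the intercurrent-event line merely explains the imputation: what is not observed after exit is taken as no response. Part of this stands. Protocol 9.4 does not settle how a partly observed window is treated, so the fault is shared. But if only missing responses became non-response, the separate strategy for leaving the study would have almost no content.

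A second reply is that the rule may sit in SAP text that cannot be read: Sections 3 and 4, Sections 5.6 and 5.7, and Appendices A and B. That cannot be excluded. The readable sections that define and analyse this endpoint contain no such rule, and SAP 2.6.3 points to none.

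A third is that the literal Protocol rule is harsh: an exit on day 165 becomes non-response with 81 of 84 days observed. That is true, and it is a reason to let the sponsor choose between the two rules, not to leave the texts unreconciled.

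A reader might also infer more than the documents support:

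- The 42% in the working counts calendar days, not patients.
- Treatment stoppers are not misclassified. Protocol 5.6.2 keeps them in the study, and their data are rightly used.
- Nothing shows that the SAP rule favours erenumab.

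**Conclusion.** The inconsistency is real, and it is limited to patients who leave the study, or are lost to follow-up, between about day 98 (94–102 with the dosing window) and the end of month 6. Earlier leavers are non-responders under both texts. The finding rests on the readable SAP and on reading the second intercurrent-event strategy as a rule in its own right.

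The effect is probably small: moving the log odds ratio by one standard error would take 12–15 net reclassified patients in one arm, if response rates lie between 30% and 60%. The number of patients and the direction cannot be determined from the documents. A stronger conclusion, that the secondary result is materially biased or that the SAP plainly overrides an unambiguous Protocol rule, is not supported. The point should be fixed because it concerns a claim-bearing endpoint and costs little.

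**What to change.** Choose one rule before unblinding.

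**A. Implement the estimand.** State in SAP 2.1.1.4 and 2.6.3 that a patient who discontinues the study or is lost to follow-up during the double-blind epoch is a non-responder, whatever month 4–6 diary data exist. Keep the available-month mean for patients still in the study, including those off treatment. Report the present available-data rule as a sensitivity analysis.

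- *Who left:* use study completion status and the primary reason for discontinuation. SAP 2.3.1 already defines this: "A patient is defined as completer for the study if study completion status on the eCRF page is ticked as not prematurely discontinued". Do not use treatment completion status, which records stopping treatment.
- *When:* the last double-blind visit or the last eDiary day, whichever is later; not the end-of-study date, nor the date on which loss to follow-up is declared.
- *Not reclassified:* patients who attended the scheduled Visit 199 (as distinct from an early final visit), or whose eDiary runs to the end of month 6, even if they later miss the safety follow-up. This matters because Visit 199 (day 169 ± 4 = 165–173) can precede the end of month 6 (up to day 172), and Protocol 5.6.1 counts such patients as completing the epoch.

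**B. Keep the available-data rule.** Amend the Protocol 9.4 estimand to match, and report the present Protocol rule as a sensitivity analysis.

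The cost of A is SAP wording and a few lines of programming on data already collected; B is a protocol wording change. Under A, response rates in both arms stay equal or fall slightly, very late exits with nearly complete data become non-response, and the treatment difference may move either way.
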